2. SYNOPSIS

Study Title	Neuroimaging Approaches to Deconstructing Acupuncture for Chronic Pain
Study Sponsor	National Institutes of Health, National Center for Complementary and Alternative Medicine Grant Number: R01AT007550
Study Objective	To evaluate the impact of acupuncture-induced somatosensory afference on altered neurobiology and analgesia in FM.
Study Design	This study design has two components: 1) a cross sectional assessment of brain chemistry, connectivity and response to pain in healthy controls and age- and sex-matched fibromyalgia patients, and 2) a longitudinal assessment of the same fibromyalgia patients randomized to either electro-acupuncture (EA) or mock laser acupuncture (ML).
Study Interventions	Electro acupuncture and mock laser acupuncture. Treatments will be delivered at 2x/week for 4 weeks, for a total of 8 treatments.
Study Duration	The study duration for healthy controls will be 1 week, with a 4 week screening window. The study duration for fibromyalgia patients will be up to 10 weeks: 4- week screening window prior to baseline; 1-week of baseline, 4 week treatment period, and 1 week of follow up.
Sample Size and Population	We will evaluate 40 healthy controls and 80 fibromyalgia patients (n=40 EA and n=40 ML). Demographics will be representative of the population of southeastern Michigan.

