3. SCHEDULE OF EVALUATIONS

3.1. Fibromyalgia Cohort

	Screening	Behavioral Session	Baseline MRI	Treatment Period	Behavioral Session	Follow-Up MRI
	Visit 0 Day -30 to 0	Visit 1 Day 0	Visit 2 Day 1-3	Visit 3-10 Day 4-32	Visit 11 Day 33-40	Visit 12 Day 34-43
Informed Consent	X					
Tender Point (1990 ACR FM Criteria)	X					
FM Survey Questionnaire (FSQ) Wolfe et al 2011 criteria for FM	X	X			X	
VAS – Pain (7day recall)	X					
FM Treatment History	X					
Medical History	X					
Vitals (Height/Weight)	X					
Urine Pregnancy Test	X	X	a		X	a
HADS	X				X	
PHQ-9 (suicidal ideation)	X	c		c	X	
Demographics	X					
Socio-demographics	X					
fMRI Screening Form		X			X	
Concomitant Medications	X	X	X	X	X	X
BPI – Severity/Interference	X	X	X		X	X
PROMIS – 29		X			X	
Perceptions of Bodily Sensations		X			X	
Pain Catastrophizing		X			X	
Credibility Scale				X	X	
PainDETECT		X			X	
Desire of Relief (DRF)		X			X	
Expected Relief Scale (ERS)		X				
MASQ (Cognition)		X			X	
Pittsburgh Sleep Quality Index (PSQI)		X			X	
VAS - Present Pain		X	X		X	X
Menstrual questionnaire		X			X	
Pain Assessment/Visual Stimulation Assessment	b	X			X	
After Cuff Questionnaire		X	X		X	X

Conditioned Pain Modulation (CPM)	b	X			X	
Neuroimaging ♦ Structural MRI ♦ Resting fcMRI ♦ Evoked Pain Test ♦ CPM (cuff) ¹ H-MRS ♦ Visual Stimulation			X			X
Randomization				X		
Treatment (EA / ML)				X		
Needling Sensations (MASS)				X		
Fibromyalgia Impact Questionnaire (FIQ-R)	X	X		X	X	
Harvard Food Diary (FFQ)		X				
Adverse Events		X	X	X	X	X
Debriefing						X

^a If not performed at behavioral session

^b Familiarization Only

^c Additional Monitoring for PHQ9 scores (10 – 14) – baseline behavioral and Treatment #3

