9.4.1. Screening

- Informed Consent review and documentation
- Review study procedures and requirements with the patient
- Collect demographic and sociodemographic information
- Record tender point count
- Complete 7-day recall VAS pain scales
- Conduct psychological screening interviews (HADS and PHQ-9). Confirm that the patient is not experiencing active suicidal ideation or intent. Any participant experiencing active suicidal ideation will be directed to seek medical help.
- Obtain medical history and fibromyalgia treatment history (*FM cohort only*)
- Conduct a physical assessment (height and weight) and confirm and document results of the Wolfe et al 2011 criteria for FM .
- Urine pregnancy test for women of childbearing potential
- Document current concomitant medications

- Collect:
 - Brief Pain Inventory - Severity and Interference scales [BPI]
 - FM Survey Questionnaire [FSQ]
 - Fibromyalgia Impact Questionnaire [FIQ-R] (*FM cohort only*)
- The Screening visit and Baseline Behavioural visit may occur on the same day.

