9.4.3. Baseline MRI – V2

- The baseline MRI is to occur within 3 days of the baseline behavioural session, but not be completed on the same day as the behavioural session.
- Review inclusion/exclusion criteria to assess patient's continued eligibility for enrolment
- Evaluate and record any changes in concomitant medications
- Urine pregnancy test (*if not performed at the behavioural session*) for women of childbearing potential
- Collect:
 - BPI
 - VAS-Present pain (pre and post MRI)
 - After-Cuff Questionnaire (*post MRI*)
- Baseline Neuroimaging (fcMIR, fMRI, and ¹H-MRS) with conditioned pain modulation and visual stimulation assessment
- Collect and record any MRI-related adverse events

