9.4.6. Follow Up MRI – V12

- Review inclusion/exclusion criteria to assess patient’s continued eligibility for enrolment
- Evaluate and record any changes in concomitant medications
- Urine pregnancy test (*if not performed at the behavioural session*) for women of childbearing potential
- Administer:
 - BPI (Severity and Interference)

- VAS-Present pain (pre and post MRI)
- After-Cuff Questionnaire (*post MRI*)
- Baseline Neuroimaging (fMRI and ¹H-MRS) with conditioned pain modulation and visual stimulation assesement
- Collect and record any MRI-related adverse events
- Complete the study close-out documentation.
- Debrief participant to their treatment assignment

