Interim analysis. After 50% of the subjects have been enrolled and evaluated, we will determine if fcMRI outcome metrics are sensitive enough to continue using for the biomarker for the duration of the study. Screening of biomarkers (brain regions) will be done by computing a post-hoc power based on 20 patients per arm. Biomarkers showing post-hoc power lower than 20% will not be pursued further. This decision corresponds to dropping biomarkers showing correlation coefficients less than 0.18 in the interim analysis.

Mediation Analysis

In the linear mixed model regressing BPI pain score on treatment and time, the effect of treatment on pain is expressed as a regression coefficient for time specific to treatment group (or a treatment by time interaction). Mediation effect will be measured as the proportion of treatment effect explained by the biomarker (PTE) representing a relative change in the regression coefficient when biomarker is included in the model (relative to the coefficient before biomarker inclusion into the model). Standard error for the PTE will be estimated by bootstrap, and a two-sided 95% interval for the effect will be constructed. Wald test with the statistic of the form (change in regression coefficient)/(bootstrap SE) will be used to test for the mediation effect. Similar analyses will be done using a logistic regression model with clinically relevant reduction in pain (defined as 50% and 30%) as a response.

Power. We use Sobel's test based on linear regression to compute power. Power analysis targets biomarkers with the mediation effect of PTE=0.5. We assume that the regression coefficient in the model for the treatment effect on connectivity is 3000; treatment effect beta in the model of change in pain excluding the biomarker is 2; standard deviation of the randomized treatment variable 0.5; standard deviation of the change in connectivity over time 4500 voxels; squared the correlation between the treatment variable and the change in connectivity $3.7e-05$; standard deviation of errors in the full model regressing change in pain on both treatment and the biomarker 1.5. These assumptions are consistent with the ones made previously in the power calculations related to different lags of the mediation analysis, with our preliminary data, and with the acupuncture effects on pain reported in the literature. Under these assumptions we will have the power of 81% to detect the mediation effect by Sobel's test.[114]

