Change in pain-evoked fMRI activation will be correlated with the change in clinical pain. To do this evoked pain responses will be added as covariates into the linear mixed model regressing BPI pain on other covariates.

Mediation Analysis is similar to the one proposed for connectivity.

11.3. Aim 3: Evaluate the ability of altered neurocircuitry at baseline to predict clinical response.

This aim evaluates a *predictive* value of the neuroimaging biomarkers by studying whether their measurements at baseline correlate with pain responses to treatments.

Hypothesis 1: Greater baseline DMN-insula/S2 connectivity and SMN-insula/S2 anti-correlation, will display greater clinical response to EA vs. ML

We will use baseline estimates of DMN and SMN connectivity, taken from the dual regression ICA analysis, as independent variable in a multiple regression model with dependent variable set as the change score (post-therapy – baseline) for clinical pain (Brief Pain Inventory; BPI). Regression slopes will be contrast between different pairs (e.g. EA vs. ML) set in the same regression model. We will explore within-group correlations for individual therapies if the difference map for any two therapies is significant, at cluster corrected $p=0.05$.

Hypothesis 2: FM patients with greater baseline insular and S2 Glx/GABA ratios will display greater clinical response to EA as compared to ML.

An identical approach will be used as for hypothesis 1 above, but with Glx/GABA ratio as dependent variable.

Hypothesis 3: FM patients with greater baseline pain-evoked insular activation will display greater clinical response to EA as compared to ML.

An ROI analysis will determine baseline insula response to evoked pain. This parameter estimate will then be used as a dependent variable in an identical multiple linear regression approach, as detailed above.

Power. The expectations for correlations between the baseline measurements of biomarkers and clinical pain responses are set similar to the mechanistic setting. We expect to uncover correlations of 0.5 between measurements at baseline and the change in pain in response to treatment (mainly in the EA arm). We will have 94% power to detect such correlations.

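### The Aim 3 BPI change score and the 30%/50% response name neither the visits nor the BPI scale; averaging the two baseline and two post-treatment readings already collected would settle this and reduce noise

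*Combined protocol and SAP*

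**What the plan says.** **Collection.** The fibromyalgia schedule in section 3.1 marks the row "BPI – Severity/Interference" at V0, V1, V2, V11 and V12. The visit lists in 9.4.1 to 9.4.6 agree: screening collects "Brief Pain Inventory - Severity and Interference scales [BPI", V1, V2 and V11 list the BPI, and V12 lists "BPI (Severity and Interference". It is not collected at the treatment visits.

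**Timing.** On the baseline side, "The baseline MRI is to occur within 3 days of the baseline behavioural session", and not on the same day. On the post-treatment side, section 3.1 gives windows of Day 33–40 for V11 and Day 34–43 for V12; section 9.4.6 sets no limit on the gap between them. The synopsis keeps the screening window apart from the rest of the study, which it describes as "1-week of baseline, 4 week treatment period, and 1 week of follow up". Section 9.4.1 adds: "The Screening visit and Baseline Behavioural visit may occur on the same day".

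**Use.** In section 11.3 the Aim 3 regressions have their "dependent variable set as the change score (post-therapy – baseline) for clinical pain (Brief Pain Inventory; BPI". In section 11.2 the mediation analysis is repeated with "clinically relevant reduction in pain (defined as 50% and 30%) as a response", and the synopsis plans a logistic regression on a 50% reduction. The Aim 2 correlation and mediation analyses use linear mixed models of BPI pain.

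**What is absent.** Section 9.2.1 introduces the BPI for both severity and interference and does not choose between them. Sections 9.2.1, 11.2, 11.3 and 11.4 do not say which visit, or what combination of visits, is baseline or post-therapy, and the response definition names no scale.

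**The concern.** A change score and a percentage response each need one number per side. The trial collects two in the baseline phase and two after treatment, so several pairs fit the wording, and the choice could be made after the data are seen. Blinding the statistician until database lock does not prevent this, because the choice can be made after lock.

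There are two consequences:

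- **Precision.** A patient-reported score varies from visit to visit. One reading per side puts the full visit error of both readings into the change, which weakens the Aim 3 slopes.
- **Classification.** A patient near the 30% or 50% cut can be a responder on one pair and a non-responder on another.

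**Working it through.** **1. The plan's own figure.** Section 11.3 states 94% power for a correlation of 0.5 between a baseline biomarker and change in pain, mainly in the EA arm (n = 40). Using the t-test of a regression slope, two-sided 0.05 (the level given elsewhere in section 11):

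ncp = √40 × 0.5 / √(1 − 0.25) = 3.65, df = 38, critical t = 2.02, power = 94.5%.

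The figure reproduces. A Fisher z calculation gives 91.6% and a bivariate-normal simulation 92.3%; neither makes the stated value wrong.

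**2. Visit pairs.** Two baseline visits (V1, V2) × two post-treatment visits (V11, V12) = 4. V0 is screening and is not counted.

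**3. Noise in the change score.** The documents give no visit-to-visit reliability for the BPI, so the following are assumptions: reliability ρ between visits in the same phase of 0.7 to 0.9, independent visit errors, total SD S and SD of true change τ.

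- Error variance per reading: σ² = S²(1 − ρ)
- Single pair: Var = τ² + 2σ²
- Mean of two per side: Var = τ² + σ²

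| S | τ | ρ | σ² | Var, single | Var, averaged | SD, single → averaged | Cut in SD |
|---|---|---|---|---|---|---|---|
| 1.7 | 1.5 | 0.7 | 0.867 | 3.984 | 3.117 | 2.00 → 1.77 | 12% |
| 1.7 | 1.5 | 0.9 | 0.289 | 2.828 | 2.539 | 1.68 → 1.59 | 5% |
| 2.0 | 1.5 | 0.7 | 1.2 | 4.65 | 3.45 | 2.16 → 1.86 | 14% |
| 2.0 | 2.0 | 0.9 | 0.4 | 4.80 | 4.40 | 2.19 → 2.10 | 4% |

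Simulating the S = 1.7 rows with scores held to 0–10 gives 1.94 → 1.71 and 1.63 → 1.55, again 12% and 5%.

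**4. What this does to Aim 3.** The plan does not say whether its r = 0.5 refers to a single-pair or an averaged change. A correlation with the change scales inversely with the SD of the change.

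- If 0.5 holds for a single pair, averaging raises it. At S = 2.0: 0.5 × √(4.80/4.40) = 0.52 to 0.5 × √(4.65/3.45) = 0.58, and power by the step 1 formula rises to 96–99%.
- If 0.5 holds only for the averaged change, a single pair lowers it to 0.5 × √(4.40/4.80) = 0.48 down to 0.5 × √(3.45/4.65) = 0.43, and power falls to 92–84%.

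**5. Responder status.** Readings were simulated at each visit and the V1/V11 classification compared with V2/V12.

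| Assumptions | 50% cut differs | 30% cut differs |
|---|---|---|
| Baseline mean 5.5, S = 1.7; true change −1.5, τ = 1.5; ρ 0.7–0.9 | 12–20% of patients | 17–27% |
| Baseline mean 5.5, S = 2.0; true change −2, τ = 1.5–2.0; ρ 0.7–0.9 | 13–24% | 16–30% |

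Overall response rates are almost the same for the two pairs. What changes is which patients count as responders.

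**6. The treatment comparison of pain, on the plan's figures.** The mediation power paragraph in 11.2 gives a treatment effect of 2, PTE 0.5, a treatment effect on connectivity of 3000, an SD of connectivity change of 4500 and a residual SD of 1.5. The implied biomarker slope is (0.5 × 2)/3000 = 1/3000. Then Var of change in pain = (4500/3000)² + 1.5² = 4.5, SD = 2.12, d = 2/2.12 = 0.94. At 40 per arm this gives about 98–99% power, so a 5–12% smaller SD could add only about 1 point.

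**The case against.** The strongest reply is that this is a small gap in specification, and that a scan-day pair (V2/V12), measured with the imaging, is as defensible as an average. Naming any one pair would indeed remove the freedom to choose. It would not recover the precision: averaging lowers the error variance whenever the two errors on a side are not perfectly correlated, and it needs no new data.

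Other parts of the reply stand and limit the point:

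- **A reader might infer that the plan discards half of its pain data.** It does not say so. The Aim 2 BPI analyses are mixed models that can take all readings, and the two-level time factor in 11.2 is stated for the connectivity model, not for the BPI.
- **A reader might count three baselines and six pairs.** The synopsis and the visit titles separate screening from baseline, and V0 may fall on the same day as V1.
- **A reader might infer bias from regression to the mean.** That would need V0 as baseline, which nothing in the plan suggests. Selection is on a VAS rather than the BPI, and the effect would fall on both randomised arms.
- **A reader might infer an underpowered EA–ML pain comparison.** Step 6 does not support that.
- **V11 and V12 are not guaranteed replicates.** Their windows allow up to 10 days between them (Day 33 to Day 43), after treatment has ended, so some disagreement may be real change in pain.

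**Conclusion.** The point holds for the Aim 3 change score and the 30%/50% response. The plan defines neither the visits nor the scale, four pairs fit its wording, and a single pair is noisier than the collected data require.

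The size rests wholly on assumed reliability. With 0.7–0.9 and independent errors, averaging cuts the SD of change by about 5–12% (4–14% at the edges of the wider assumptions), and responder status differs between V1/V11 and V2/V12 in roughly 12–30% of patients. Read these as upper-end values: errors at visits one to three days apart may be positively correlated, which acts like a higher reliability, and part of any V11–V12 difference may be genuine.

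No stated power is wrong. No loss is shown for the Aim 2 mixed models; what they lack is a statement of which BPI visits enter.

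**What to change.** In 9.2.1 and 11.2–11.3, state:

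- The clinical pain outcome is BPI pain severity.
- Baseline is the mean of V1 and V2, and post-treatment is the mean of V11 and V12, using the single available value if one is missing. V0 is for screening only.
- These values define both the Aim 3 change score and the 30%/50% response.
- The BPI visits that enter the Aim 2 mixed models are listed.
- The mediation models with and without the biomarker use one identical BPI outcome. PTE is the relative change in a single treatment coefficient and is not coherent if the outcome differs between the two models.
- Scan-day values (V2, V12) may be kept as a sensitivity analysis for the same-day pain–biomarker correlation.

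The cost is wording only, with no added visit or questionnaire. The downside is interpretive: because V11 and V12 may be some days apart, the post-treatment mean describes pain over the follow-up period rather than on one day.

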 - **Hypothesis 3:** EA will more readily reduce pain-evoked fMRI activation in the insula as compared to ML, which will not reduce pain-evoked fMRI activation. The change in pain will correlate with change in insula response to evoked pain for EA but not ML.
- ◆ **Aim 3. Evaluate the ability of altered neurocircuitry at baseline to predict clinical response to electro- and mock laser acupuncture**
- **Hypothesis 1:** FM patients with greater baseline DMN-insula positive correlation and SMN-insula anti-correlation will display greater clinical response to EA. There will be no predictive value for ML – which is an inert form of sham acupuncture with no somatosensory afference.
 - **Hypothesis 2:** FM patients with greater baseline insular Glx/GABA ratios will display greater clinical response to EA. There will be no predictive value for ML.
 - **Hypothesis 3:** FM patients with greater baseline pain-evoked insular activation will display greater clinical response to EA. There will again be no predictive value for ML.

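### Aim 3 reads the within-arm correlations only after a significant EA–ML slope difference in the same patients, which biases the reported EA correlation upward and the ML correlation downward when the difference favours EA

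*Combined protocol and SAP*

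**What the plan says.** Section 11.3, Hypothesis 1, regresses the change in BPI pain on baseline DMN and SMN connectivity. The comparison of arms is a slope contrast: "Regression slopes will be contrast between different pairs (e.g. EA vs. ML) set in the same regression model". The within-arm step follows conditionally: "We will explore within-group correlations for individual therapies if the difference map for any two therapies is significant", with the map judged at a cluster-corrected 5% level. No region is named from which the within-arm values would be taken.

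Hypothesis 2 (baseline Glx/GABA ratio) and Hypothesis 3 (evoked-pain activation) are said to use the same approach as Hypothesis 1. For Hypothesis 3 the measure comes from a region of interest: "An ROI analysis will determine baseline insula response to evoked pain". Section 9.3.3 also mentions correlating baseline activation with change in pain, without any gate.

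The power statement for Aim 3 concerns a correlation of 0.5, expected mainly in the EA arm: "We will have 94% power to detect such correlations". Section 5 adds a hypothesis about the other arm: "There will be no predictive value for ML". Cross-validation appears in Section 11 only for the Aim 1 ROC analysis.

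**The concern.** The slope contrast and the two within-arm correlations come from the same 80 patients. A contrast passes the threshold more readily when chance has raised the EA association and lowered the ML association. Correlations that are looked at only after the contrast has passed carry that chance component with them.

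The distortion has the same shape as the Aim 3 hypotheses: prediction in EA, none in ML. A real but modest ML association could be reported as near zero, and an EA association could be reported as stronger than it is. Section 6 presents these results as a guide to which patients benefit from which form of acupuncture, so the sizes of the within-arm estimates matter to readers.

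**Working it through.** **Inputs.** From the documents: 40 patients per arm (Synopsis); true correlation 0.5 in EA (Section 11.3, Power); 0 in ML (Section 5, Aim 3); significance at 5%. Assumed, because not stated for this step: a two-sided test, no dropout, and, for a searched map, 10 to 60 independent elements with a Bonferroni threshold. Correlations are expressed as strength in the hypothesised direction; with change scored as post minus baseline, the raw sign may be negative.

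**1. The plan's own figure.** For r = 0.5 and n = 40, the noncentrality is 0.5/√(1 − 0.25) × √40 = 3.65. With critical t = 2.024 on 38 df, power is 94.5%. Using √38 instead gives 3.56 and 93.4%; direct simulation gives about 92%. The stated 94% is reproduced. It is power for an ungated correlation.

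**2. Without the gate.** Simulated mean correlations at 0.5/0 are 0.495 (EA) and 0.00 (ML): essentially unbiased.

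**3. With the gate.** Let z = atanh(r), with variance 1/(40 − 3) in each arm. The difference D = z(EA) − z(ML) has SD s = √(2/37) = 0.2325 and mean μ = atanh(ρ_EA) − atanh(ρ_ML). A result favouring EA passes when D > z_c·s. Given passing, D exceeds its mean on average by s·λ(a), where a = z_c − μ/s and λ(a) = φ(a)/(1 − Φ(a)). The arms have equal variance, so each takes half: z(EA) rises and z(ML) falls by h = s·λ(a)/2.

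Example, 0.5/0 in a fixed region: μ = 0.549; a = 1.960 − 0.549/0.2325 = −0.403; λ = 0.560; h = 0.2325 × 0.560/2 = 0.065. EA: tanh(0.549 + 0.065) = 0.55. ML: tanh(−0.065) = −0.065.

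| True EA/ML | Read from | z_c | a | λ | h | Formula EA / ML | Simulated EA / ML |
|---|---|---|---|---|---|---|---|
| 0.5/0 | fixed region | 1.960 | −0.403 | 0.560 | 0.065 | 0.55 / −0.07 | 0.54 / −0.06 |
| 0.5/0 | 10 elements | 2.807 | 0.444 | 1.101 | 0.128 | 0.59 / −0.13 | 0.59 / −0.12 |
| 0.5/0 | 60 elements | 3.341 | 0.979 | 1.508 | 0.175 | 0.62 / −0.17 | 0.62 / −0.17 |
| 0.3/0 | fixed region | 1.960 | 0.629 | 1.237 | 0.144 | 0.42 / −0.14 | 0.42 / −0.14 |
| 0.3/0 | 10 elements | 2.807 | 1.476 | 1.918 | 0.223 | 0.49 / −0.22 | 0.48 / −0.22 |
| 0.3/0 | 60 elements | 3.341 | 2.010 | 2.382 | 0.277 | 0.53 / −0.27 | 0.52 / −0.27 |

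Testing the slope contrast in one regression model (76 df) instead of on the Fisher scale gives 0.54 / −0.07 for the first row.

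**4. A real ML association.** At true 0.5/0.2, a fixed region gives about 0.58 / 0.07, and 10 to 60 searched elements give about 0.64 to 0.67 / 0.00 to −0.05. The ML association shrinks or vanishes.

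**5. A smoothed map.** A 12×12×12-voxel smoothed map with cluster-forming p < 0.001 and the cluster extent set to 5% family-wise error gives cluster means of 0.59 / −0.19 at 0.5/0 and 0.50 / −0.27 at 0.3/0. Map size, smoothness and forming threshold are assumptions, but the direction and rough size agree with the table.

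**The case against.** Requiring a significant contrast before looking within arms is a recognised safeguard against claiming a difference because one arm is significant and the other is not. All three Aim 3 hypotheses in Section 11.3 are worded as EA against ML, and the gate leaves that test untouched. The within-arm step is presented as exploratory. All of this stands, and it limits the point to the within-arm estimates. It does not remove it: the power statement is about a correlation, and the Section 5 claim about ML can only be examined within the ML arm.

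Several stronger readings are tempting but not supported.

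- *That the correlations are read only where the map is significant.* The text says *if*, not *where*. With a fixed region the bias at the plan's own values is modest, about +0.05 for EA and −0.06 for ML.
- *That the pattern would typically appear when both arms predict equally.* At a true 0.3 in both arms, a falsely significant result favouring EA does yield a striking pair (about 0.52 / 0.04 in a fixed region). It arises in only about 2.5% of trials in a fixed region and up to about 3% with a searched map.
- *That Hypothesis 3 escapes through its region of interest.* The region removes the spatial search. If the same approach carries the gate over, the conditioning on significance remains, as the fixed-region rows show.

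**Conclusion.** The concern holds for the within-arm correlations and goes no further. Given a significant difference favouring EA, they are biased in the direction of the Aim 3 hypotheses. At 0.5/0 with 40 per arm the averages are about 0.54 and −0.06 from a fixed region, or 0.59 to 0.62 and −0.12 to −0.17 from searched elements. The bias grows as the true effect shrinks: at 0.3/0, about 0.42 and −0.14, or 0.48 to 0.52 and −0.22 to −0.27. A significant difference favouring ML would bias both the other way.

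The direction follows from the gate alone. The size depends on where the values are read, which the plan leaves open, and on the assumed number of elements. A reader might infer that the Aim 3 comparison of arms is compromised; it is not, because the slope contrast is tested before any selection. The gate may also apply to Hypotheses 2 and 3. Hypothesis 2 has no map in the literal sense, so the wording there needs settling too.

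**What to change.** In Section 11.3:

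- Keep the slope contrast in the joint model as the test of EA against ML.
- Define anatomical regions in advance for each Hypothesis 1 target: insula for DMN, insula for SMN, and S2. An insula-only region would miss S2, which Hypothesis 1 in Section 11.3 also names. The middle-insula region used for power in Section 11.1 concerns DMN in patients versus controls, and the SMN pilot finding in Section 9.3.1 concerns the anterior insula, so one region will not serve for all.
- Report both within-arm correlations with confidence intervals from those regions, and from the Glx/GABA ratio and the evoked-pain region for Hypotheses 2 and 3, whether or not the contrast or map is significant.
- Use the voxel map for location only.

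The cost is a change of SAP wording and one extracted mean value per region per scan. The reported correlations will look less striking.

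### Aim 3's only power figure (94%) fits a correlation within one 40-patient arm; the planned EA-versus-ML slope contrast has about 63–72% for the single-value biomarkers (H2, H3)

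*Combined protocol and SAP*

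**What the plan says.** Section 11.3 words all three Aim 3 hypotheses as comparisons of EA with ML. Hypothesis 3, for example, reads "FM patients with greater baseline pain-evoked insular activation will display greater clinical response to EA as compared to ML".

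The analysis is set out under Hypothesis 1. The baseline biomarker is the independent variable and change in BPI pain is the response. The test is then described as follows: "Regression slopes will be contrast between different pairs (e.g. EA vs. ML) set in the same regression model". Within-arm correlations come second and are conditional: "We will explore within-group correlations for individual therapies if the difference map for any two therapies is significant".

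Hypotheses 2 and 3 refer back to this model:
- Hypothesis 2: "An identical approach will be used as for hypothesis 1 above, but with Glx/GABA ratio as dependent variable".
- Hypothesis 3: "This parameter estimate will then be used as a dependent variable in an identical multiple linear regression approach".

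The power paragraph sets its expectations by analogy with Aim 2 and assumes correlations of 0.5 between the baseline measurements and "the change in pain in response to treatment (mainly in the EA arm" (the parenthesis closes there). It concludes "We will have 94% power to detect such correlations". No other power figure is given for Aim 3. For the ML arm, Section 5 predicts "There will be no predictive value for ML".

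**The concern.** The stated power and the planned test do not match. A power of 94% for r = 0.5 describes one correlation in one arm. The hypotheses are decided by a difference between two slopes, and the standard error of that difference carries the uncertainty of both arms. A significant EA correlation beside a non-significant ML one would not show that the slopes differ.

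A reader who takes 94% as the power of the Aim 3 test will misread a null result. At 63–72% power, the contrast misses the plan's own expected effect in about 28–37% of trials. A non-significant contrast would then look like strong evidence against prediction when it is not.

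The plan does power an EA-versus-ML slope difference elsewhere (Section 11.2, Hypothesis 3, 40 per group), so the omission in Aim 3 departs from its own practice.

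The variable roles are a second inconsistency. As literally written, Hypotheses 2 and 3 regress a baseline biomarker on later pain change. That is not the model of Hypothesis 1, and it does not fit an aim of predicting clinical response.

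**Working it through.** **Inputs**
- 40 patients per arm (Section 2, Synopsis). Section 11.3 makes no allowance for dropout, so all 40 are taken as evaluable.
- r = 0.5 in EA (Section 11.3, Power) and r = 0 in ML (Section 5, Aim 3).
- Two-sided 0.05. This is stated for Aim 1; Section 11.3 gives only a cluster-corrected 0.05 for Hypothesis 1, so it is an assumption for Hypotheses 2 and 3.
- The biomarker is a single value per patient, with no other covariates.

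**Step 1: reproduce the 94%.** For one arm, the noncentrality is r/√(1−r²) × √n = 0.5/√0.75 × √40 = 3.65 on 38 df. Power is 94.5%. Treating the biomarker as random gives 92.1% by simulation, and Fisher's z gives 91.6%. With all 80 patients the power would be 99.9% (noncentral t). The stated figure is therefore a single-arm figure.

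**Step 2: power of the slope contrast.** Scale the biomarker to SD 1; the interaction test has 76 df.
- *Equal outcome SD in both arms.* The slopes are 0.5 and 0, and the residual variances are 0.75 and 1 (mean 0.875). Noncentrality = 0.5/√(0.875 × 2/40) = 2.39; power 65.6%. Simulation with a random biomarker gives about 63%.
- *Equal residual SD in both arms.* The slope difference is 0.5/√0.75 = 0.577 residual SDs. Noncentrality = 0.577/√(2/40) = 2.58; power 72.2%. Simulation gives about 69.5%.
- *Fisher's z for two correlations.* atanh(0.5)/√(2/37) = 0.549/0.2325 = 2.363; power = Φ(2.363 − 1.960) = 65.6%.

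The range is about 63–72%. Against the printed 94% the gap is 94 − 72 = 22 to 94 − 63 = 31 points. Comparing like with like, it is 22–29 points with a fixed predictor (94.5 against 65.6–72.2) and 23–29 points with a random predictor (92.1 against 62.8–69.5).

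**Step 3: the gated sequence.** The probability that both the contrast and the EA correlation are significant, by simulation, is 61.9% (equal outcome SD) and 68.5% (equal residual SD).

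**Step 4: sensitivity of the contrast power**

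| Scenario | Power |
|---|---|
| EA 0.5, ML 0, 40 per arm | 63–72% |
| EA 0.5, ML 0.1 | 45–56% |
| EA 0.5, ML 0.2 | 28–38% |
| EA 0.6, ML 0 | 80–91% |
| EA 0.5, ML 0, 36 per arm (assumed 10% dropout; no rate is given) | 58–68% |
| EA 0.5, ML 0, one-sided test | 74–80% |

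For the contrast itself to have 94% power at 40 per arm with ML at 0, the EA correlation would have to be about 0.62–0.69.

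**Step 5: variable roles.** Hypothesis 1 has the biomarker as independent variable and BPI change as response. Hypotheses 2 and 3 make the biomarker the dependent variable and call the approach identical. Both cannot hold. Taken literally, the reversed model gives a contrast power of 62.5% and 56.2% under the two SD structures, so the literal reading does not rescue the 94% either.

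**The case against.** The power sentence is open about what it covers. It speaks of correlations, mainly in EA, and never claims to be the power of the contrast. Section 5 words the Aim 3 hypotheses as prediction of response to EA with none for ML. The opening of Section 11.3 and the evoked-pain analysis in Section 9.3.3 also speak of correlating baseline measures with pain change. For the EA half of that wording, 94% is the matching figure. This stands as a description of the sentence: the number is not miscalculated. It does not supply power for the planned test, which is a slope contrast for all three hypotheses.

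The 63–72% is also conditional. The word mainly allows some correlation in ML, which lowers power. Aim 2, the model for these expectations, speaks of at least 0.5, which could raise it. Both directions are in the table. An ML correlation of zero is the plan's own prediction and is kinder to the plan than any positive value.

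The gate is explicit only for Hypothesis 1's difference map and reaches Hypotheses 2 and 3 only through the word identical. The gated figures are therefore secondary, and the conclusion does not depend on them.

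Finally, the interim paragraph of Section 11.3 ranks the predictive analysis below the mechanistic one. That limits the consequence to how Aim 3 results are read.

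**Conclusion.** The concern holds. The 94% is right for a single correlation of 0.5 in 40 patients, but the planned Aim 3 test is an EA-versus-ML slope contrast with about 63–72% power for Hypotheses 2 and 3. The lower end takes a random biomarker and equal outcome SDs; the upper end takes fixed biomarker values and equal residual SDs. The range rests on r = 0.5 against 0, 40 completers per arm, a two-sided 0.05 level, and a single-value biomarker without cluster correction.

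It does not cover Hypothesis 1's cluster-corrected map, which cannot be powered from the documents. Nor does it cover the logistic regression on 50% pain reduction in the Synopsis, for which no power is stated. The reversed variable roles in Hypotheses 2 and 3 are a plain contradiction with Hypothesis 1. This should be fixed, but it does not affect whether the trial can run.

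**What to change.** 1. In Section 11.3, state the power of the EA–ML slope contrast for Hypotheses 2 and 3 as about 63–72% at r = 0.5 against 0. List the assumptions: ML correlation, SD structure, 40 completers per arm, single-value biomarker, no cluster correction. Add the lower values for an ML correlation above 0, and say that Hypothesis 1's map is not covered by the figure.
2. Label the 94% as the power of an ungated correlation within the EA arm only.
3. Correct Hypotheses 2 and 3 so that the baseline biomarker is the independent variable and change in BPI is the response, as in Hypothesis 1.

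The cost is wording. The stated Aim 3 power becomes less favourable; no patients, visits or analyses are added.
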